6.2 Investigational medical device (IMD)

6.2.1 Packaging, labelling and storage

Each device will be provided in a folding box containing one glass syringe prefilled with 1.0 mL of the injectable gel implant and two 27G $\frac{1}{2}$ " disposable sterile needles, and a product leaflet (Instructions for Use; IFU¹⁶). Additionally, cannulas (25G x 50mm and 22G x 70mm) will be provided.

Two labels showing the batch number are attached to the boxes. One of these should be attached to the subject's medical record. IMDs from the two different manufacturing sites (see section 2.2) can separately be identified and differentiated by investigator. The IMD is labeled according to applicable guidelines and national legal requirements indicating that the device is exclusively for use in a clinical investigation.

The IMD must be stored in the original box, at 2-25°C (36-77 °F) in a dry place, protected from light, heat and frost. The shelf life of finished sterilized Saypha® FILLER Lidocaine is 24 months at the specified storage conditions.

The investigator must ensure that upon receipt of the IMD and other study supplies, these are kept in an appropriate and secure location, with access limited to authorized individuals.

6.2.2 Methods of use

Prior to administration

 Prior to administration, the subjects should be evaluated for any possible contraindications or risks and should be informed of all possible risks and warnings associated with treatment (also refer to section specified in the IB¹¹).

Preparation for administration

- The skin to be treated should be thoroughly cleaned and disinfected prior to injection of the device and appropriate aseptic technique should be employed throughout the procedure.
- Prior to use the device, the luer-lock adapter should be held securely and the tip cap should be removed by twisting and pulling carefully, which should prevent formation of bubbles. The syringe should be held and the enclosed needle / cannula firmly attached. The needle / cannula should be secured tightly by twisting clockwise. The syringe is held correctly if the backstop opens at the back, toward the hand in which it is held. These steps are illustrated in the Instructions for Use (IFU).

Injection technique

The IMD should be injected into the submucosa of the lips²³. Superficial injections, near the interface of the epidermis and papillary dermis, can result in visible white, yellow, or blue nodules, which may be persistent. Deep injections into the subcutaneous fat may result in loss of the filler in the vast subcutaneous space, requiring larger volumes.

After insertion of the needle / cannula, and just before injection, the plunger rod should be withdrawn slightly to aspirate and verify that the needle is not intravascular.

The 27G $\frac{1}{2}$ " needle or either 25G x 50mm cannula or 22G x 70mm cannula, which are provided with the kit, have to be used. A minimum of 30 subjects will be treated either with 27G $\frac{1}{2}$ " needle or cannula (25G x 50mm or 22G x 70mm cannula).

The technique used is essential for the success of the treatment. The following injection techniques should be employed based on investigator's preference and characteristics of the defect under correction.

These include:

Retrograde technique: introduction of the entire needle / cannula along the wrinkle or skin depression and injecting while slowly withdrawing the needle / cannula.

Bolus technique: deposition of a small bolus just before withdrawing the needle. Placing the bolus on mucosa in the white portion of the lip and under the muscle is absolutely necessary. The bolus injections are placed subdermal from the white portion of the lip directly into the mucosa. If a larger volume of the filler is needed to achieve the correction, small volumes should be injected in two sessions, instead of high volumes in one session. The device should be injected slowly with the least amount of possible pressure for the same reason.

If the needle / cannula is blocked, the pressure on the plunger rod should not be increased, but the injection stopped and the needle /cannula replaced.

The injection must be stopped just before the needle / cannula is pulled out of the skin to prevent leakage of the device or placement too superficially in the skin.

In case of a vascular event, injection must be stopped immediately, and high dose hyaluronidase, massage and heat (gauze with hot water) should be applied. In addition, nitroglycerin paste may encourage vasodilatation. ¹⁹

In case of any other adverse event the Expert Consensus Recommendations for treatment of Soft Tissue Filler Complications¹⁹ should be followed in the discretion of the investigator. More details are provided in section 6.2.6.

The remainder of the IMD from the same syringe after application to one lip can be used for the application to the other lip of the same subject at the same visit but not for any other subject or any other visit of the same subject. Note: If the remaining IMD from one syringe will be used for the application to the other lip, the injection volume for the first lip must be documented beforehand (see section 6.4.6).

Completion of administration

After injection the investigator may apply a light massage for uniform distribution of the filler.

Application of ice packs for 5-10 min. post injection and after subject's pain assessment has been performed (see section 6.4.8) is optional and may reduce redness and swelling.

In order to identify potential AEs (e.g., possible blanching caused by arterial occlusions) post-administration a safety evaluation by the investigator after 15 minutes needs to take place. Therefore, the subject should be requested to stay on site for at least 15 minutes after the injection.

Prior to discharge the subject should be advised to follow restrictions specified in section 6.3.7 and to inform their investigator as soon as possible about any unwanted event, especially inflammatory reactions persisting for more than one week or any other occurring secondary effect (also refer to section 14).

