5.1 Objectives

The main objectives of this investigation are:

- To evaluate the effectiveness, safety and long-term safety of Saypha® FILLER Lidocaine for lip augmentation;
- To assess the duration of the aesthetic effect of Saypha® FILLER Lidocaine for lip augmentation.

Additional objectives:

- To compare the effectiveness of Saypha® FILLER Lidocaine ('IMD-HQ' and 'IMD-C1') produced in the two different manufacturing sites ('HQ' and 'C1').
- To compare the IMD injection techniques 'retrograde technique' and 'bolus technique'
- To compare the injection equipment used: '27G ½" needle' versus cannula ('25G x 50mm cannula' or '22G x 70mm cannula')

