5.2 Hypotheses

This is a non-comparative study and does not entail formal hypothesis testing.

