6.1.2 Randomization

Subjects providing written informed consent and having met all inclusion and none of the exclusion criteria will be randomized in a 1:1 ratio to one of the two IMDs (either IMD from manufacturing site 'HQ' or 'C1') (see section 2.2 for details). The site staff can perform the randomization via the eCRF sytem and distribute the respective IMD ('IMD-HQ' and 'IMD-C1') to the subjects accordingly.

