7.1.2 Additional Objectives

1. To compare the effectiveness of Saypha® FILLER Lidocaine ('IMD-HQ' and 'IMD-C1') produced in the two different manufacturing sites ('HQ' and 'C1').
2. To compare the IMD injection techniques: 'retrograde technique' and 'bolus technique'
3. To compare the injection equipment used: '27G ½" needle' versus cannula ('25G x 50mm cannula' or '22G x 70mm cannula')

8 Study Design

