10.8 Subgroup Analyses

Besides the ‘overall population’ (including all subjects enrolled in the investigation), which includes all enrolled subjects, the following subgroups will descriptively be analyzed:

- **IMD from manufacturing sites: ‘HQ’ and ‘C1’**
 IMD from two different manufacturing sites (‘C1’ and ‘HQ’) will be used and subjects will be randomly assigned in a 1:1 ratio to ‘IMD-C1’ or ‘IMD-HQ’, respectively.
 Subgroup analysis will compare both IMDs (‘IMD-HQ’ or ‘IMD-C1’) and separately analyze the results for the ‘IMD-C1’ and ‘IMD-HQ’ subgroups.
 Summary of subgroup analysis will compare both IMDs (‘IMD-HQ’ or ‘IMD-C1’) will be analyzed descriptively using FAS populations
- **Injection technique: ‘retrograde technique’ and ‘bolus technique’**
 Subgroup analysis will separately analyze the results for subjects treated with the two different injections techniques.
 Summary of different injections techniques will be analyzed descriptively using FAS populations
- **Injection equipment: ‘27G ½” needle’ versus cannula (‘25G x 50mm cannula’ or ‘22G x 70mm cannula’)**
 Subgroup analysis will separately analyze the results for subjects treated by means of the different injection equipment.
 All subgroup analyses are planned to be performed for the primary performance endpoint and the main secondary performance endpoints.

All subgroup analyses are planned to be performed for the primary performance endpoint and the main secondary performance endpoints using FAS population only.

The following secondary performance endpoints are planned to be analyzed:

- The percentage of responders, based on the investigator live assessment at 6, 12 and optional 18 months after the initial treatment using the validated LFS.

- The percentage of responders based on the independent photographic reviewer’s assessments before initial treatment and at Week 6, Month 6, 12 and optional Month 18 after initial treatment, based on photographs and using the validated LFS.
- The percentage of subjects with an improvement relative to baseline photographs, (subjects who have been rated as “very much improved” or “much improved” or “improved”), based on the investigator assessment at Week 6, Month 6, 12 and optional Month 18 after initial treatment using the 5-point GAIS.

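### Injection technique and equipment are not randomised, so the crude subgroup summaries cannot answer the objectives to compare them

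*Protocol*

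**What the plan says.** **Objectives.** SAP 7.1.2 lists "To compare the IMD injection techniques" as an additional objective, and Protocol 5.1 adds "To compare the injection equipment used". Protocol 5.2 states: "This is a non-comparative study and does not entail formal hypothesis testing".

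**Allocation.** Under Protocol 6.1.2 subjects "will be randomized in a 1:1 ratio to one of the two IMDs"; nothing else is randomised. Protocol 6.2.2 says that the techniques "should be employed based on investigator's preference and characteristics of the defect under correction". Of the needle and the two cannulas it says only that these, "which are provided with the kit, have to be used". Protocol 6.2.2 and 7.3.10 add a minimum of 30 subjects for needle or cannula, without saying how they are selected.

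**Rating.** The primary endpoint is the investigator's live Lip Fullness Scale (LFS) grade at Week 6 (Protocol 6.1.1), and blinding is marked as not applicable (6.1.3). An independent reviewer also grades photographs (6.1.4, 6.4.7), and the synopsis calls that review blinded.

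**Analysis.** SAP 10.8 states: "Subgroup analysis will separately analyze the results for subjects treated with the two different injections techniques". The equipment analysis is worded in the same way. Both are limited to the Full Analysis Set, and no covariate is named. Protocol 7.3.9 and SAP 10.7.4 rule out site stratification because of the limited number of subjects. SAP 10.9 plans a sensitivity analysis of the site effect on the primary endpoint, without a method and without a link to these subgroups.

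**The concern.** With at most three sites, an investigator's preferred technique, the person injecting and the person grading may largely coincide. Technique also follows the defect, and eligible lips range from grade 1 to grade 3 (Protocol 6.3.3). A crude difference between retrograde and bolus, or between needle and cannula, could then be a site, operator, rater or baseline effect and still be reported as the answer to a stated objective. Calling the summary descriptive does not change what the difference contains.

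Two further gaps add to this:

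- Protocol 6.2.2 describes the retrograde technique with needle or cannula but the bolus technique with the needle only. The two contrasts may therefore be partly the same contrast.
- Technique and equipment are recorded at each treatment (Protocol 6.2.4, 6.4.6), and SAP 10.5 covers initial and touch-up treatment. SAP 10.8 has no rule for a subject whose technique or equipment changed, so group membership would be decided after the data are seen.

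**Working it through.** **1. The plan's own precision figures.** Protocol 7.1 assumes a 90% responder rate. The 95% half-width is 1.96 × √(p(1−p)/n).

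- n = 100: 1.96 × √(0.09/100) = 0.0588, stated as 0.059.
- n = 50: 1.96 × √(0.09/50) = 0.0832, stated as 0.083.

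Both reproduce. They cover the overall population and the manufacturing subgroups. No precision is stated for technique or equipment.

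**2. Sampling error of a crude contrast, with 90% in both groups.** The half-width is 1.96 × √(0.09/n₁ + 0.09/n₂).

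- 30 against 70: 1.96 × √(0.0030 + 0.0012857) = 0.128.
- 50 against 50: 1.96 × √(0.0036) = 0.118.

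**3. Spurious difference with no true effect.** The documents give no responder rate by site, rater or baseline grade, so the rates here are assumptions. Take two equal strata with response p_H and p_L. A share s of technique A and 1−s of technique B falls in the higher stratum. The crude difference is then (2s−1)(p_H − p_L).

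| Split of technique across strata | Strata 95% and 85% | Strata 98% and 82% |
|---|---|---|
| 60/40 | 0.2 × 10 = 2 points | 0.2 × 16 = 3.2 points |
| 70/30 | 0.4 × 10 = 4 points | 0.4 × 16 = 6.4 points |
| 80/20 | 0.6 × 10 = 6 points | 0.6 × 16 = 9.6 points |
| 90/10 | 0.8 × 10 = 8 points | 0.8 × 16 = 12.8 points |
| Complete separation | 10 points | 16 points |

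Both pairs of strata average 90%, the planning rate. At the upper end the bias is about as large as the sampling error in step 2, and a larger sample would not reduce it.

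**4. What stratification could recover.** Take two sites of 55 and a 90/10 split, so 49.5 and 5.5 subjects per technique within each site. 1/49.5 + 1/5.5 = 0.2020. With equal site weights the standard error of the site-stratified responder difference is ½ × √[0.2020 × (p₁(1−p₁) + p₂(1−p₂))].

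- Sites at 98% and 85%: ½ × √[0.2020 × (0.0196 + 0.1275)] = 0.086, half-width 1.96 × 0.086 = 0.17.
- Sites at 95% and 85%: ½ × √[0.2020 × (0.0475 + 0.1275)] = 0.094, half-width 0.18.

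A full stratification has 3 sites × 3 grades × 2 techniques = 18 cells, about 110/18 = 6 subjects each. If each site uses one technique, a within-site difference cannot be estimated at all.

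**The case against.** The strongest reply is that these are additional objectives in a study that declares itself non-comparative. The results are to be summarised descriptively, with no test and no claim of superiority or equality planned for technique or equipment. The statement in Protocol 6.1.4 that no difference is to be shown concerns the manufacturing sites only. All of this is correct, and it limits how serious the point is. It does not remove the mismatch between an objective to compare and a summary that cannot attribute a difference.

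The plan also has safeguards. The photographic LFS is read away from the sites, in a single session (SAP 11), and is among the endpoints analysed by technique and equipment. Subject-rated aesthetic improvement and pain are also on that list. A reader might infer that the investigator's dual role affects every subgroup result; the documents do not support that. What remains is selection by defect and operator differences between sites, which central grading cannot remove. The SAP 10.9 site analysis is not tied to technique or equipment.

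A reader might also infer that equipment is chosen by preference and defect. The sentence in Protocol 6.2.2 covers technique only; for equipment the documents show no randomisation and no rule, and nothing more.

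Finally, site stratification was dropped for lack of subjects, and step 4 bears that out. A demand for full site-by-grade stratification would not be reasonable.

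**Conclusion.** The point holds as a limit of design and analysis. The crude summaries in SAP 10.8 cannot separate a technique or equipment effect from site or operator, baseline lip grade and, for investigator-rated endpoints, the rater. Technique and equipment may also be confounded with each other.

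The documents do not show that bias will occur, or how large it would be. The range of 2 to 10 points rests on assumed strata of 95% and 85% with no true effect; strata of 98% and 82% give 3.2 to 16. It would be wrong to read any one of these figures as the expected error. The primary estimate in the overall population and the randomised manufacturing comparison are not affected. The plan should be amended because two stated objectives would otherwise be answered by contrasts that cannot carry them.

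**What to change.** In SAP 10.8:

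1. Cross-tabulate technique and equipment by site, by baseline LFS grade and against each other.
2. Beside the crude summaries, estimate the difference in LFS change adjusted for site and baseline LFS as main effects, for both investigator and photographic LFS. State that it is not estimable where technique or equipment coincides with site. Baseline grade may not capture everything meant by the defect, so residual confounding should be acknowledged.
3. Classify each subject by technique and equipment at initial treatment. Show subjects whose use differs between lips or at touch-up as a separate mixed category. Classify per lip only if the eCRF records technique and equipment per lip: Protocol 6.4.6 says so explicitly for volume alone.
4. Reword the two objectives in SAP 7.1.2 and Protocol 5.1 so that they describe results by technique and equipment, with no claim of superiority or equality.

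The cost is a few more tables, a wording change (by written amendment for the Protocol) and wide intervals where cells are sparse: about 17 points half-width for a site-stratified responder difference in the 98% and 85% case of step 4. No new data are needed for the subject-level version, and injection practice does not change.

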6.2.3 Applied volume of the device

Saypha® FILLER Lidocaine is administered by injection into the lips. The volume applied depends on the size of the area which requires correction and will be selected by the investigator. A maximum volume of 2 mL for both lips in total (i.e., for upper plus lower lip)²³ might be needed per treatment (i.e., initial treatment and touch-up treatment, respectively) but the maximum recommended volume is up to 10 mL per treatment session and up to 20 mL per subject per year; these amounts include potential touch-up treatments (also see section 6.4.6).

6.2.4 Touch-up treatment

A touch-up treatment may be performed at the Week 3 visit (Visit 2) at the investigator's discretion, if correction is not deemed satisfactory after the first injection at Visit 1.

If applicable, it will be documented in the subject's records and the eCRF with the same level of details as the initial treatment (see section 6.4.6 for details).

6.2.5 Precautions and warnings for the investigator

Refer also to the current IB¹¹ (esp. sections 8.1.5 and 8.1.6) and to the IFU¹⁶:

- The device must only be used by qualified medical healthcare personnel trained on the respective injection technique.
- The device must be injected into non-inflamed, disinfected, healthy skin.
- After use the syringe, needle /cannula and remaining contents should be disposed after use in a special container and the device shall never be re-used.
- The device should not be re-used; quality and sterility can only be guaranteed for a syringe in its original package; Re-use of the device creates potential infection risk for subjects or users.
- Verify the integrity of the syringe and expiry date before use. The device must not be used if the
 expiry date has lapsed, or if the packaging or contents are damaged. Syringes with an open or
 shifted tip cap within the protective packaging must not be used. In such case follow instructions
 given in section 14.8.
- The device should only be used with the syringe, the needle or the additionally provided cannula provided by the manufacturer.
- The needle / cannula must not be manipulated or bent. If the needle / cannula is blocked, do not increase the pressure on the plunger rod but stop the injection and replace the needle. Discard the needle /cannula in a special container
- There are no available clinical data (effectiveness, tolerance) about injecting the device into an area which has already been treated with another filling product.
- The device should not be injected into blood vessels, bones, tendons, ligaments, nerves, muscles
 or naevi. The treating physicians should be familiar with the face's vascular anatomy to avoid the
 incidence of arterial inclusion. During the pretreatment planning phase, proximity of susceptible

vessels to common treatment areas should be considered, being aware that anatomical location of blood vessels can vary between different subjects.

- Overcorrection should be avoided.
- The device should never be placed in contact with quaternary ammonium compounds (such as benzalkonium chloride solutions) or with medical-surgical instruments that have been in contact with these substances.
- The device shall not be used in women who are pregnant or breastfeeding (see section 6.3.7 for more information).
- Subjects should be advised to follow restrictions as given in section 6.3.7.
- Subjects must be advised to inform their investigator as soon as possible about any unwanted event. Special focus should be on inflammatory reactions persisting for more than one week or any other occurring secondary effect. The investigator should treat these side effects appropriately¹¹ and document as AE in the subject's medical record and in the eCRF (see section 14 for more details).

6.2.6 Rescue medication

Any rescue medication / procedure applied should be documented in the subject's medical record and in the eCRF as concomitant medication/prodcedure (see section 6.4.3).

Use of Hyaluronidase

In case of overcorrection or occurrence of nodules (see IB¹¹, section 8.2.2) or vascular compromise (see IB, section 8.2.3), a commercially available hyaluronidase injection (e.g. , or similar) may be used at the discretion of the investigator.

In case impending tissue necrosis, which may occur with any dermal filler, a recent consensus statement on the treatment of hyaluronic acid filler-induced impending necrosis recommends immediate treatment with high doses of hyaluronidase (e.g., at least 200 units of equivalent), followed by warm compress, vigorous massage and topical nitroglycerin paste. If no improvement is seen within 60 minutes, additional quantities of hyaluronidase should be injected (3-4 cycles in total). An oral aspirin regimen (e.g., 650 mg per day) should help prevent further clot formation. Daily follow-up is advised. If no improvement or progression of necrosis is observed, the above regimen of hyaluronidase, nitroglycerin paste and aspirin should be repeated daily, typically for 2-3 days. ¹⁹

In case of any other adverse event the Expert Consensus Recommendations for treatment of Soft Tissue Filler Complications should be followed in the discretion of the investigator. The current Expert Consensus Recommendations for treatment of Soft Tissue Filler Complication are filed in the Investigator's File. ¹⁹

